### **Data Collection Techniques and Instruments**

Clinical Record Information Collection The following information will be obtained from each participant's clinical record:

- Sociodemographic Background: o Gender o Age o Ancestry o Education
- Medical Background o Time within the cardiovascular health program o Morbid history o Medications and dosage o Time using medications o Laboratory tests (fasting glucose, glycosylated hemoglobin, lipid profile)

### **Physical Activity Level and Quality of Life**

The international physical activity questionnaire (IPAQ) (40) will be applied to estimate the level of physical activity prior to the intervention. Health-related quality of life will be measured using the SF36 questionnaire (41) before and after the intervention.

Physical Function Physical function will be measured through the Six-Minute Walk Test, and grip dynamometry.

#### **Six-Minute Walk Test**

The Six-Minute Walk Test (6MWT) is a simple and effective submaximal exercise test used to assess aerobic functional capacity, especially in patients with cardiopulmonary and respiratory diseases. The main objective of this test is to measure the distance an individual can walk over a span of six minutes on a flat, hard surface. This test is widely used because it is easy to perform, does not require sophisticated equipment, and reflects activities of daily living.

The general protocol of the 6MWT includes the following steps:

1. Preparation: Before the test, the procedure is explained to the patient, and consent is obtained. Baseline measurements such as heart rate, blood pressure, and oxygen saturation should be recorded.
2. Instructions: The patient is instructed to walk at their own pace but to try to cover the greatest distance possible in six minutes. They are allowed to slow down or stop if necessary.
3. Conducting the Test: During the test, the patient walks along a marked hallway, turning around at the end of each stretch. The evaluator follows the patient to assist if necessary but without encouragement to not influence performance.
4. Post-test: Immediately after the test, heart rate, blood pressure, and oxygen saturation are re-measured. The total distance covered is also recorded.
5. Results Analysis: The distance walked is compared to reference values based on the patient's age, gender, and other variables to assess their functional capacity.

### Grip Dynamometry

Grip strength will be assessed using the CAMRY Model EH101 dynamometer (46) following the Southampton protocol. The procedure begins with the subject seated with forearms resting on the chair, the wrist just over the end of the chair arm, in a neutral position, with the thumb up and feet flat on the floor, they are asked to squeeze the dynamometer as hard as they can for as long as they can. Three attempts will be made with each hand and the best attempt of the 6 total will be recorded (47).

### Metabolic Flexibility – Indirect Calorimetry

To assess the balance of energy substrates during exercise, indirect calorimetry measurement will be used; this measurement provides minute-to-minute energy expenditure data that make it the most valuable tool for distinguishing the various components of energy expenditure associated with the energy cost of a given activity (48).

## **Body Composition and Waist Circumference**

Height will be measured using a precision stadiometer 0.1 cm (Seca Bodymeter 206) (49), weight, percentage of fat and lean mass will be measured using a bioimpedance meter (TANITA BC-534) (50). BMI will be estimated using the kg/m^2 formula. Waist circumference will be measured at the midpoint between the costal margin and the iliac crest, with a non-deformable precision tape measure 0.1 cm Seca 201(49). It will be performed in a standing position, and at the end of a normal expiration.

## **Cardiovascular Parameters**

Systolic and diastolic blood pressure and heart rate will be measured using an automatic monitor (Omron HEM 7130™; Omron Healthcare Inc., Lake Forest, IL) (51) at rest following the standard seated procedure after 15 minutes of rest, being done before and after 15 min of each session.

## **Metabolic Parameters**

Fasting glucose, cholesterol, and triglyceride values will be obtained through tests requested in the controls of the Cardiovascular Health Program.

## **Pain Intensity**

The Chronic Pain Grading Scale will be applied to assess pain intensity (52).

## **Pressure Pain Threshold**

The Pressure Pain Threshold (PPT) is defined as the minimum amount of pressure that elicits the first sensation of pain, and will be measured using a pressure algometer (53).

## **Pain Characterization**

The modified DN4 questionnaire will be applied to determine the characteristics of pain prior to the intervention (54).

## **Adaptation Capacity to Workload**

The capacity to adapt to workloads will be evaluated through the changes observed in the tests described above at four times: pre-intervention, week 4, week 8, and post-intervention (week 12).

## **High-Intensity Interval Training (HIIT)**

During HIIT, 8-10 intervals/session will be performed on a cycle ergometer, at an intensity of 80-100% of the theoretical maximum heart rate (MHR) according to Karvonen, equating to a bicycle load of 8 to 10 points on the modified Borg scale of 1-10 points (55). Each interval will consist of 1 minute of cycling, followed by 2 minutes of inactive rest, similar to previous protocols (27). Every two weeks, the bicycle load will be adjusted (increasing the resistance to pedaling of the bicycle) due to normal physiological adaptations and improvement of the patient's baseline threshold, always exercising the patient in each effort interval at a muscular intensity of 8 to 10 points according to the modified Borg scale similar to previous studies (27).

## **Resistance Exercise with Elastic Materials (REM)**

During REM, participants will perform concentric and eccentric contractions with Theraband CLX elastic bands for 1 minute at an intensity of 8-10 according to the OMNI-RES scale. The rest period will last 2 minutes and each exercise will be repeated 3 times. Three exercises will be performed: bicep curls, horizontal rowing in a chair, and wide squat. The exercise load will be modified every two weeks according to the physiological adaptations of the subjects to the training, in order to adjust the loads to the new thresholds and always work at an intensity of 8-10 on the OMNI-RES scale.

### **Control Group:**

Participants in the control group will be requested to maintain their current lifestyle and exercise habits throughout the duration of the study. This includes adhering to their usual regimen of prescribed medication.

## **Statistical Analysis**

The sample size will be calculated as follows: (1) ANOVA for repeated measures with intra-inter-group interaction, (2) three groups, (3) type I error: 5%, (4) type II error: 20%, (5) statistical test power: 80%, and (6) effect size (ES): 0.10 according to Cohen's classification (1988). Using these parameters, the total sample size recommended by G\*Power software (Version 3.1.9.2) was 174 (58 per group). Assuming a 10% dropout, the total was calculated at 192, with 64 participants randomly assigned to each group. The concealment of allocation will be conducted by a researcher not involved in the clinical procedures of the intervention using the

method of opaque, sealed, and consecutively numbered envelopes. The random sequence and allocation concealment allow for the control of selection bias.

For enhanced bias control, the data analysis will be performed by a researcher blinded to the intervention groups. Dependent variables will be described in terms of mean and standard deviation. Assumptions of normality and homoscedasticity for all data will be verified using the Shapiro-Wilk test and the Levene's test, respectively. To address General Objective 1, the Student's t-test will be used to detect baseline differences between groups, and a repeated measures ANOVA (group x time) to determine differences in all dependent variables between training prior, and at 4, 8, and 12 weeks afterwards. The Bonferroni post hoc test will be used to test differences between groups. Additionally, the Cohen's d test will be applied to determine the effect size. To address the General Objective, the Pearson correlation test will be used to determine the relationship between MHR and the presence and intensity of non-oncological chronic pain. The level for statistical significance was set at  $p < 0.05$ . Statistical analyses will be performed using SPSS software version 21 (SPSS™ Inc., Chicago, IL, USA).

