### **Inclusion and Exclusion Criteria**

Inclusion: a) Being physically inactive (not performing 300 or 150 min of moderate or vigorous intensity physical activity respectively per week measured with the IPAQ questionnaire); b) BMI between 25 and 39.9 kg/m^2; c) Belonging to the cardiovascular health program of the External CESFAM of Valdivia d) Presenting with or without non-oncologic chronic pain.

Exclusion: a) Bone disease; b) Ischemic disease or arrhythmia and c) Chronic respiratory disease d) Uncontrolled chronic diseases f) People unable to understand instructions, g) People who do not speak Spanish h) History of previous oncological disease or under study for suspected neoplastic disease in any part of the body i) Low adherence to training (< 70% or non-attendance at 4 continuous sessions).

Included users will be divided into 3 groups: HIIT, ERE, and Control. All subjects will be evaluated at four times: pre-intervention (week 0 – time 1), week 4 (time 2), week 8 (time 3), and post-intervention (week 12 – time 4). Only the evaluation of metabolic flexibility and direct oxygen consumption will be carried out pre (week 0) and post-intervention (week 12).

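### Metabolic flexibility, direct oxygen consumption and SF36 are measured only twice, so the four-time ANOVA does not fit them and the stated 80% power does not carry over to them automatically

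*Combined protocol and SAP*

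**What the plan says.** The Statistical Analysis section of the combined protocol and SAP bases the sample size on "ANOVA for repeated measures with intra-inter-group interaction" with three groups, a 5% type I error, "statistical test power: 80"% and "effect size (ES): 0.10". The G*Power total "was 174 (58 per group"). On attrition it adds: "Assuming a 10% dropout, the total was calculated at 192". The number of measurements, the correlation between them and the sphericity correction are not among the listed inputs. The same section then applies a group by time repeated-measures ANOVA, with times before training and at 4, 8 and 12 weeks, to every dependent variable.

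The visit schedule is not the same for every variable. Inclusion and Exclusion Criteria begins with a general rule, "All subjects will be evaluated at four times", and then makes an exception: "Only the evaluation of metabolic flexibility and direct oxygen consumption will be carried out pre (week 0) and post-intervention (week 12"). Physical Activity Level and Quality of Life adds a third two-visit outcome: "Health-related quality of life will be measured using the SF36 questionnaire (41) before and after the intervention". The Work Plan agrees: Month 3 lists SF36 and metabolic flexibility before the intervention, and the four-weekly evaluation in Months 4 to 6 names only cardiometabolic variables and pain.

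No separate analysis or power statement covers these three outcomes.

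**The concern.** There are two mismatches. The first does not depend on any calculation: an ANOVA with four levels of time cannot be fitted to an outcome that has two. The analyst would have to choose the model for these outcomes later, without guidance from the plan.

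The second concerns power. If 174 was obtained for four measurements, its 80% refers to a four-measurement test. The plan puts no limit on which outcomes that figure covers and names no primary outcome. A null result for metabolic flexibility, oxygen consumption or quality of life could then be read as though the trial had a known 80% chance of detecting the planned effect on it. These outcomes are not incidental. The problem statement expects the exercise programme to improve metabolic flexibility, and Expected Results anticipates better quality of life.

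**Working it through.** **Inputs.** From Statistical Analysis: k = 3 groups, alpha = 0.05, effect size 0.10 (read as Cohen's f), N = 174. From the visit schedule: m = 4 measurements for most outcomes and m = 2 for the three named above. Assumed, because the plan is silent: correlation rho = 0.5 (varied below) and sphericity epsilon = 1.

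**Formula** (noncentral F, G*Power form for the within-between interaction, epsilon = 1): lambda = f² × N × m / (1 − rho), df1 = (k − 1)(m − 1), df2 = (N − k)(m − 1).

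**1. Reproducing the plan's figure.** With m = 4 and N = 174, lambda = 0.01 × 174 × 4 / 0.5 = 13.92, df = 6 and 513, and power is 80.4%. At N = 171 it is 79.6%. The smallest total with equal groups is therefore 174, as stated. At the same rho, m = 2 needs 246, m = 3 needs 204 and m = 5 needs 153.

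This match does not prove that m was 4. With f = 0.10, a total of 174 also results from m = 2 with rho 0.65, m = 3 with rho 0.57, or m = 5 with rho 0.43. Four measurements at rho = 0.5 is the most plausible reading because it fits the visit schedule, but it is an inference.

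**2. Two measurements, f held at 0.10.** With m = 2, N = 174 and rho = 0.5, lambda = 0.01 × 174 × 2 / 0.5 = 6.96, df = 2 and 171, and power is 64.5%. If all 192 were evaluable it would be 69.1%. Power at N = 174 over the unstated correlation:

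| rho | m = 4 | m = 2 |
|---|---|---|
| 0.3 | 63% | 49% |
| 0.4 | 71% | 56% |
| 0.5 | 80.4% | 64.5% |
| 0.6 | 90% | 75% |
| 0.7 | 97% | 87% |

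Two measurements reach 80% at rho of about 0.645.

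**3. Two measurements, week-12 difference held fixed.** In this formula f measures the spread of interaction effects over all group by time cells, so the same week-12 difference gives a different f when the number of visits changes. Let the effect at each visit be a fraction of its week-12 value, and let V be the variance of those fractions over the four visits. With only weeks 0 and 12 the fractions are 0 and 1, with variance 0.25. Then f at two visits = 0.10 × √(0.25 / V). At N = 174 and rho = 0.5:

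| Fractions at weeks 0, 4, 8, 12 | V | f, two visits | Power, two visits |
|---|---|---|---|
| 0, 1/3, 2/3, 1 | 0.139 | 0.134 | 89% |
| 0, 0.5, 0.8, 1 | 0.142 | 0.133 | 88% |
| 0, 1, 1, 1 | 0.1875 | 0.115 | 78% |
| 0, 0, 0, 1 | 0.1875 | 0.115 | 78% |
| 0, 0, 1, 1 | 0.25 | 0.100 | 64.5% |

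Fractions confined to 0 to 1 cannot have a variance above 0.25, so 64.5% is the floor under this convention at rho = 0.5. The 89% is the highest of the five patterns tried.

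**4. ANCOVA for the two-visit outcomes.** With equal variance at both visits, a change score has variance 2σ²(1 − rho) and the ANCOVA residual has variance σ²(1 − rho²). The ratio is (1 + rho) / 2, so lambda is multiplied by 2 / (1 + rho). At rho = 0.5, lambda = 6.96 / 0.75 = 9.28 and power is 77.6%. At f = 0.10 and N = 174:

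| rho | Two-time ANOVA | ANCOVA |
|---|---|---|
| 0.3 | 49% | 69% |
| 0.5 | 64.5% | 78% |
| 0.7 | 87% | 92% |

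**The case against.** The strongest reply is that 64.5% is produced by a convention. It keeps f at 0.10 while the number of visits changes, and f does not mean the same thing at two visits as at four. For an effect that builds up gradually, which is plausible for training, the two-visit test has more power than the four-visit omnibus test, because it spends 2 numerator degrees of freedom instead of 6. This stands. It rules out quoting 65% as the power of the design for these outcomes. It does not show that 80% applies to them either: the answer depends on a trajectory and a correlation that the plan does not give.

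A second reply is that sizing a trial on its main four-visit outcomes is ordinary practice. General Objective 1 and its specific objectives name cardiometabolic risk factors, physical function and chronic pain, and none of the three two-visit outcomes. Nor does the plan expressly claim 80% for each variable. This also stands, and it keeps the point modest. It does not answer the first mismatch, since the Statistical Analysis section assigns the four-time ANOVA to every dependent variable.

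A third reply is that a group by time ANOVA with two levels of time is a valid analysis, so omitting ANCOVA is not an error. That is correct. The plan does not specify the two-level version, however, and ANCOVA had more power at every correlation tried.

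**Conclusion.** The point holds as a modest improvement. The four-time ANOVA cannot be run as written for metabolic flexibility, direct oxygen consumption and SF36. This follows from the visit schedule alone and rests on no assumption.

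The 80% does not transfer automatically to these outcomes. At f = 0.10, N = 174 and two measurements, power is 64.5% at rho = 0.5, with a range of 49% to 87% for rho from 0.3 to 0.7. With the week-12 difference fixed and rho = 0.5, it runs from 64.5% to 89% over the trajectories tried. Both ranges assume epsilon = 1.

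A reader might infer three stronger things that the documents do not support:

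- That 174 is an arithmetic error. It is reproduced exactly under settings that fit the visit schedule.
- That 174 can come only from four measurements. Other pairs of m and rho give the same total.
- That the trial has 65% power instead of 80% for the two-visit outcomes. That figure needs both rho = 0.5 and f fixed at 0.10 across different numbers of visits. The plan states no rho and does not say how its effect size applies to a two-visit outcome.

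**What to change.** In the Statistical Analysis section:

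- Name the analysis for metabolic flexibility, direct oxygen consumption and SF36: ANCOVA on the week-12 value, with group as factor and the week-0 value as covariate. Keep the four-time ANOVA for outcomes measured four times.
- State the number of measurements, the correlation and the sphericity correction used in G*Power, and say that the 80% refers to outcomes measured four times. If the inputs were not four measurements, 0.5 and 1, give the actual ones.
- Give power for the two-visit outcomes under the chosen analysis, with its assumed correlation and effect definition, as a range and not as a single 65%. For ANCOVA at f = 0.10 and N = 174, this is 69%, 78% and 92% at correlations of 0.3, 0.5 and 0.7.

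The cost is a few sentences in the plan. No participants, visits or measurements are added, since the week-0 value is already collected. The power statement becomes longer and, for these outcomes, conditional on stated assumptions.

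### The 192 to be randomised falls about one expected completer short of the plan's own 174 at the stated 10% dropout; the effect on power is negligible

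*Combined protocol and SAP*

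**What the plan says.** The sample-size paragraph under Statistical Analysis bases the calculation on "ANOVA for repeated measures with intra-inter-group interaction", with three groups, a 5% type I error, "statistical test power: 80"%, and "effect size (ES): 0.10 according to Cohen's classification (1988"). It reports that "the total sample size recommended by G\*Power software (Version 3.1.9.2) was 174 (58 per group"). The allowance for losses follows directly: "Assuming a 10% dropout, the total was calculated at 192, with 64 participants randomly assigned to each group".

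The number of measurements is not in that paragraph. It is given under Inclusion and Exclusion Criteria: "All subjects will be evaluated at four times: pre-intervention (week 0 – time 1), week 4 (time 2), week 8 (time 3), and post-intervention" at week 12. The plan does not state the correlation between repeated measures, the non-sphericity correction (epsilon), or the formula that takes 174 to 192. No other section gives a different dropout rate or sample size.

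**The concern.** The 192 has one purpose: to leave 174 participants with usable data after the assumed losses. Dropout is ordinarily a fraction of those enrolled, and read that way the two figures do not agree, since 90% of 192 is less than 174. The pattern is that of adding 10% to the required number instead of dividing that number by the 90% expected to remain.

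The number of completers matters here because the planned analysis is a repeated measures ANOVA over four visits. In its classical form it uses only participants with complete data, and the section names no method for missing data. What is at stake is the accuracy of the enrolment figure, which will be carried into reports. The stated power would be at stake only if the shortfall were large.

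**Working it through.** **Inputs from the plan.** Three equal groups (k = 3), alpha 0.05, power 80%, effect size 0.10 (taken as Cohen's f), 174 required (58 per group), 10% dropout, and 192 randomised (64 per group), all from Statistical Analysis. Four measurements (m = 4) come from Inclusion and Exclusion Criteria.

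**Assumed, because the plan does not state them.** Correlation between repeated measures rho = 0.5 and epsilon = 1. They affect only the power figures in steps 1 and 4.

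**Step 1. Reproduce 174.** For the group-by-time interaction, power comes from the noncentral F distribution with

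- lambda = f² x N x m / (1 - rho)
- df1 = (k - 1)(m - 1) = 2 x 3 = 6
- df2 = (N - k)(m - 1)

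At N = 174, lambda = 0.01 x 174 x 4 / 0.5 = 13.92, df2 = 171 x 3 = 513, and power is 80.4%. The smallest N that reaches 80% is 173, and the smallest multiple of three is 174. The plan's figure is reproduced.

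**Step 2. Reproduce 192 and 64.**

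| Route | From 174 in total | From 58 per group |
|---|---|---|
| Multiply by 1.10 | 191.4, rounded up to 192 | 63.8, rounded up to 64 |
| Divide by 0.90 | 193.3, rounded up to 194 | 64.4, rounded up to 65 (195 in total) |
| Stated in the plan | 192 | 64 |

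Multiplication matches both stated figures and division matches neither. This is a strong inference about the route, but still an inference.

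**Step 3. Apply the stated loss to the stated enrolment.** This step needs neither rho nor epsilon, and it does not depend on how 192 was reached.

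- Expected completers in total: 192 x 0.90 = 172.8
- Expected completers per group: 64 x 0.90 = 57.6
- Shortfall: 174 - 172.8 = 1.2 in total, and 58 - 57.6 = 0.4 per group
- Largest dropout that still leaves 174: 1 - 174/192 = 9.4%
- For comparison, 195 x 0.90 = 175.5

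Two quantities should be kept apart. The expected shortfall in completers is about 1. The gap in the enrolment target is 194 - 192 = 2, or 195 - 192 = 3 with equal groups.

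**Step 4. Effect on power** (same model as step 1).

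| Completers | Power |
|---|---|
| 172 | 79.9% |
| 172.8 (expected) | 80.1% |
| 173 | 80.2% |
| 174 | 80.4% |

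The expected loss of power is 80.4 - 80.1 = 0.3 percentage points.

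**Step 5. How much the unstated inputs matter.** With rho = 0.45 the smallest N for 80% power is 190, and with rho = 0.55 it is 156. With epsilon = 0.9, power at 174 is 77.1%. A change of 0.05 in rho therefore moves the required N by 17 in either direction, against 1.2 completers here.

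**The case against.** The strongest defence is that the plan never says what the 10% is a percentage of. Adding 10% to the required number is a common shorthand. If it means losing 10% of 174, which is 17.4 people, then 192 - 17.4 = 174.6 and the target is met. This stands in part. The plan prints no formula, so the multiplication route can only be inferred, and 64 x 3 = 192 is consistent in itself. But the allowance is described as dropout and is applied to the number randomised, where the usual denominator is those randomised. If another denominator was meant, the text should say so.

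A second objection is that nothing of consequence changes. This stands. The planned 80% power is still met at the expected number of completers, and the difference is far smaller than the uncertainty from the unstated correlation and epsilon.

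A third objection is that moving to 195 would not secure the sample, because the 10% rate is given without support. The problem statement reports that adherence to some aerobic programmes falls by as much as 50% within three months, and the exclusion list includes low adherence to training. At 15% loss, 195 leaves 165.8 and 192 leaves 163.2, so both miss 174. This also stands, and it is why the larger target is optional.

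A reader might infer that the trial is underpowered, or that it is 2 to 3 completers short. The documents support neither. The 2 to 3 is the gap in the enrolment target, and the expected completer shortfall is 1.2. Power falls just below 80% only if 172.8 is rounded down to 172; the nearest whole number is 173, which gives 80.2%.

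**Conclusion.** The point holds as a minor arithmetic correction. Taking dropout as a fraction of those randomised, 192 gives 172.8 expected completers against the 174 required. It covers losses of at most 9.4%, not the stated 10%. That result uses only the plan's own figures.

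The statement that power is essentially unaffected (80.1% against 80.4%) rests on the assumed rho = 0.5 and epsilon = 1. These values reproduce the plan's 174 but do not appear in it. The multiplication by 1.10 is inferred from its exact match to both 192 and 64. Only the claim that 192 allows for a 10% loss needs correcting; no analysis or conclusion of the trial changes.

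**What to change.** Amend one sentence in Statistical Analysis. Any of these would do:

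- **Keep 192 and describe what it delivers.** State that 192 randomised (64 per group) gives about 173 expected completers (57 to 58 per group) and about 80% power at 10% loss, and state the correlation and epsilon used (0.5 and 1, if the sponsor confirms that these are the values behind 174).
- **Keep 192 and correct the rate.** State that 192 covers about 9.4% dropout.
- **Optional: raise the target to 195 (65 per group).** At 10% loss this leaves 175.5 expected completers.

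The first two cost only the wording. The third costs three more participants, one per group, and the effect on power does not make it necessary. In each case the sentence should say that the dropout percentage is of those randomised.

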Regarding non-oncologic chronic pain, it is recognized as a disease in its own right (15), with a prevalence of 32.1% in the Chilean population (16), becoming a public health issue, negatively impacting quality of life, user function, representing a high socioeconomic burden (17, 18). Some metabolic disorders (e.g., diabetes mellitus, hypertension, and obesity) have been linked to the development and progression of non-oncologic chronic pain (9, 10, 11). Furthermore, individuals with non-oncologic chronic pain and cardiovascular diseases experience greater pain severity and disability than those with chronic pain alone (19). People with chronic pain often experience functional limitation, which is associated with low levels of physical activity, sedentary behavior, increasing the risk of developing cardiovascular diseases (19).

In this context, individuals with CRFs may enter the Cardiovascular Health Program (PSCV), which aims to reduce the incidence of cardiovascular events through the control and compensation of CRFs in primary care through the following actions:

- Reducing the cardiovascular risk of controlled individuals.
- Promoting healthy lifestyles.
- Achieving control of risk factors.
  - Achieving optimal blood pressure levels.
  - Improving metabolic control in people with diabetes.
  - Improving cholesterol levels in individuals with dyslipidemia.

Complementing the actions of the PSCV, physical exercise becomes a cornerstone for the control of these CRFs (20), improvement in metabolic flexibility (21), and reduction of non-oncologic chronic pain associated with CRFs (22, 23). Moderate-intensity aerobic exercise for 30 to 60 minutes every day of the week has been described as the most used alternative for controlling these risk factors (24); however, achieving this volume of exercise is very difficult in a clinical setting. Since lifestyle change is not easy for the population, adherence to some aerobic exercise programs decreases up to 50% in the first 3 months (25). Factors responsible for this low adherence include session duration, the presence of disease or post-exercise pain, and lack of time reported by users (26).

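### The planned four-visit repeated measures ANOVA has no missing-data method; as normally run in SPSS it drops anyone missing one visit, losing power and risking bias if losses differ by arm

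*Combined protocol and SAP*

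**What the plan says.** The Inclusion and Exclusion Criteria section sets the schedule: "All subjects will be evaluated at four times: pre-intervention (week 0 – time 1), week 4 (time 2), week 8 (time 3), and post-intervention". The last of these falls at the end of the 12-week programme. Some outcomes are exceptions. "Only the evaluation of metabolic flexibility and direct oxygen consumption will be carried out pre (week 0) and post-intervention (week 12"), and under Physical Activity Level and Quality of Life, "Health-related quality of life will be measured using the SF36 questionnaire (41) before and after the intervention".

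The Statistical Analysis section gives one model for Objective 1: "a repeated measures ANOVA (group x time) to determine differences in all dependent variables between training prior, and at 4, 8, and 12 weeks afterwards". On software it says "Statistical analyses will be performed using SPSS software version 21" and names no procedure. The only provision for lost data is in the sample size: "Assuming a 10% dropout, the total was calculated at 192, with 64 participants randomly assigned to each group". The document states no analysis population, no missing-data method and no sensitivity analysis.

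Two places bear on who may be lost. The Problem Statement reports that adherence to certain aerobic programmes falls by as much as half within three months, and adds: "Factors responsible for this low adherence include session duration, the presence of disease or post-exercise pain, and lack of time reported by users". The exclusion list includes training attendance under 70%, or four sessions missed in a row. That can be known only once training has started, and only in the HIIT and ERE arms.

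**The concern.** A classical repeated measures ANOVA needs a value at every time level. The usual SPSS procedure for it deletes a participant who lacks one. For a four-visit outcome, someone who leaves after week 8 contributes none of three recorded values, and someone who attends weeks 0, 8 and 12 but misses week 4 is also removed.

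Two things are at stake. The first is power, because the sample size budgets for withdrawal but not for missed interim visits among people who finish. The second is the validity of the exercise-versus-control comparison. If people whose outcomes worsen leave more often from the exercise arms, the completers are selected by outcome and differently by arm, and the early values that would show this are discarded.

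**Working it through.** **Plan's own figure.** Inputs from Statistical Analysis: k = 3 groups, f = 0.10, alpha = 0.05, power 80%. From the visit schedule: m = 4. The document gives neither the between-visit correlation (rho) nor the sphericity correction, so I assumed rho = 0.5 and epsilon = 1. For the group x time interaction:

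- lambda = f² × N × m / (1 − rho) = 0.01 × 174 × 4 / 0.5 = 13.92
- df1 = (k − 1)(m − 1) = 6; df2 = (N − k)(m − 1) = 513
- power from the noncentral F = 80.4%

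N = 174 is also the smallest equal-arm total reaching 80% under these settings, so the plan's figure is reproduced. With m = 4, rho = 0.3 would need 243 and rho = 0.7 would need 105.

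**Withdrawal alone.** 192 × 0.90 = 172.8 complete cases, power 80.1%. This loss is already budgeted, with almost no slack.

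**Missed interim visits.** Let a fraction q of those remaining miss each of weeks 4 and 8, independently. The document gives no rate; these are assumptions. Complete cases = 172.8 × (1 − q)².

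| q | Complete cases | Power, rho 0.5 | Power, rho 0.6 | Power, rho 0.7 |
|---|---|---|---|---|
| 0 | 173 | 80.1% | 89.3% | 96.7% |
| 2% | 166 | 78.2% | 87.8% | 96.0% |
| 5% | 156 | 75.1% | 85.4% | 94.6% |
| 10% | 140 | 69.5% | 80.6% | 91.7% |

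At rho = 0.3 even 174 complete cases give only 63.5%.

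A likelihood-based analysis of all available visits (rho 0.5, data missing completely at random, the 10% dropout spread evenly after weeks 0, 4 and 8, covariance treated as known) has power 81.6%, 81.3% and 81.0% at q = 0, 5% and 10%.

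**Bias with no true effect.** Simulated outcomes had SD 1 and rho 0.5 at four visits; plus means exercise is favoured. With dropout more likely the more a participant had worsened by week 4, at 12–28% in the exercise arms against 5% in controls, the complete-case difference in change from baseline was about +0.05 to +0.15 SD. Raw week-12 means were nearly unbiased in this setting. The distortion is in change from baseline, which is what the interaction tests.

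A second simulation removed the worst changers outright, at stated rates per arm:

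| Loss, exercise v control | Complete case, leaving depends on observed change | Complete case, leaving depends on unseen week-12 change | Likelihood model, observed | Likelihood model, unseen |
|---|---|---|---|---|
| 10% v 10% | about 0 | about 0 | about 0 | about 0 |
| 20% v 10% | +0.08 | +0.15 | about 0 | +0.12 |
| 30% v 10% | +0.15 | +0.30 | about 0 | +0.24 |
| 10% v 20% | −0.08 | −0.16 | about 0 | −0.12 |

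**Scale.** With two exercise arms and one control arm, 12–28% against 5% is an overall dropout of (2 × 12 + 5)/3 = 9.7% to (2 × 28 + 5)/3 = 20.3%. Only the lower end matches the planned 10%. With 156 complete cases (52 per arm) and SD of change √(2 × (1 − 0.5)) = 1, the standard error of a two-arm difference is √(2/52) = 0.196. A bias of 0.05 SD is about a quarter of that; 0.15 SD is about three quarters.

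**The case against.** Several points on the other side stand.

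- **Deletion is inferred.** SPSS 21 also has a mixed-model procedure, and the plan does not rule it out. But the plan names repeated measures ANOVA, and the sample size was calculated for that test. If a mixed model was meant, the text should say so.
- **The rates are assumed.** The whole power shortfall comes from missed-visit rates that the document does not give and from rho = 0.5. At rho = 0.6 or above, even 140 complete cases keep 80%. That is correct, but 0.5 is the value that reproduces the plan's 174.
- **The adherence passage is general.** It concerns exercise programmes at large, and it also lists session length and lack of time, which need not depend on outcome. It makes heavier, outcome-driven loss in the exercise arms plausible, as does the attendance criterion; neither establishes it.

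Stronger readings are tempting, and the document does not support them. A reader might infer that the ANOVA is bound to favour exercise, or does so whenever people leave because they worsened. It does so only if such loss is heavier in the exercise arms. A reader might infer that a participant with a missed visit loses all their data. Deletion is per outcome, and a missed week 4 or 8 leaves SF-36, metabolic flexibility and oxygen consumption untouched. A reader might also infer that the expected 10% withdrawal itself breaks the 80% power; it does not.

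**Conclusion.** The concern holds in a limited form. The plan has no missing-data method, and its named test, run in the usual way, analyses only participants with all four values of the outcome concerned.

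The cost in power is nil if loss stays at 10% in total. It reaches about 2, 5 or 11 percentage points below 80% if 2%, 5% or 10% also miss each interim visit at rho 0.5. The possible bias towards exercise is about 0.05 SD at overall dropout near the planned 10%, and up to about 0.15 SD at roughly twice that. It depends on outcome-driven loss being heavier in the exercise arms, and its sign follows the imbalance.

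A mixed model recovers most of the lost power and removes the bias explained by recorded values. It removes only a minor part of bias from loss driven by unseen values (+0.15 falls to +0.12, +0.30 to +0.24). It should be adopted, but it is not a complete remedy.

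**What to change.** In Statistical Analysis, for outcomes measured at four visits, replace the repeated measures ANOVA with a linear mixed model for repeated measures: group, visit and group x visit, unstructured covariance, REML (the MIXED procedure in SPSS 21). Include every recorded visit of every randomised participant, and visits after training stops where they are recorded. Take the week-12 group contrasts from that model as change from baseline.

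Also:

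- report dropout and missed visits by arm and reason;
- keep the complete-case ANOVA as a sensitivity analysis;
- add a sensitivity analysis for data not missing at random, such as shifting the values assumed for exercise-arm leavers by stated amounts.

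The cost is plan wording and some extra analysis, with the same software and no added participants or visits. The model relies on a missing-at-random assumption, which is weaker than the one the complete-case ANOVA makes. Systematically assessing people after they stop training would go further than this, because the document makes no provision for it; that would change trial conduct, and the fix does not depend on it.
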